	
 
Use of medium-acting antihistamines (hydroxyzine, loratadine, etc.) more than one time within 7 days of DBPCFC or skin testing.*
 
Use of systemic steroid medications (IV, IM or oral) for indications other than asthma for > 3 weeks within the past 6 months
 
Use of beta-blockers (oral), (ACE) inhibitors, angiotensin-receptor blockers or calcium channel blockers.
 
Participation in any trials of therapeutic interventions for food allergy in the past year.
 
Therapy with anti-IgE or other biologics, including within 1 year of enrollment.
 
Use of investigational drugs within 52 weeks of participation.
 
Allergy to all of the following: oat, rice, corn, tapioca.
 
Pregnancy
 
Past or current medical problems or findings from physical examination or laboratory testing that are not listed above, which, in the opinion of the investigator, may pose additional risks from participation in the study, may interfere with the participant's ability to comply with study requirements or that may impact the quality or interpretation of the data obtained from the study.
 
*Any subject meeting these criteria during the visits can be rescheduled for the oral food challenge or prick skin testing.
 

Study Stopping Rules	The study will be temporarily suspended pending DSMB review if
	any of the following occurs
	
 
Any death possibly related to study participation .
 

	• 2 subjects requiring more than 1 injection of epinephrine for at home study-allowed ingestion of peanut.
	
 
3 subjects diagnosed with eosinophilic esophagitis
 

Participant Stopping Rules	Participants may be prematurely terminated from the study for the following reasons:
	
 
The participant elects to withdraw consent form all future study activities, including follow-up.
 
The participant is "lost to follow-up" (i.e., no further follow-up is possible because attempts to reestablish contact with the participant have failed.
 
The participant dies.
 
The Investigator no longer believes participation is in the best interest of the participant. This includes subjects who refuse to come for the Desensitization DBPCFC visit.
 

	
 
Subjects who fail to adhere to the request to stop the study intervention per section 6.5 will be considered for premature termination.
 
Pregnancy
 
Diagnosis of eosinophilic esophagitis
 

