### 8.4 Unscheduled Visits

If disease activity increases or other concerns arise between regularly scheduled visits, participants will be instructed to contact study personnel and may be asked to return to the study site for an "unscheduled" visit. If the participant becomes/is unable to ingest at least 1/8 teaspoon of peanut butter, they will undergo a supervised feeding of 1/16th teaspoon, which is the lowest amount permitted and may become the daily amount if tolerated. If the participant cannot ingest 1/16th teaspoon of peanut butter they will be considered a treatment failure and will stop any daily ingestion, but will undergo the endpoint DBPCFCs at 72 weeks.

The following circumstances may lead to unscheduled visits (active arm):

1. Concern regarding peanut ingestion triggering increased chronic symptoms (e.g., increased eczema, gastrointestinal symptoms).

Procedures (1-8 hour visit):

- Physical exam, vital signs, medical history
- Spirometry (or peak flow under age 7, or if spirometry not allowed per COVID protocols)
- DBPCFC to the amount being ingested on a daily basis, or supervised open feeding of the amount ingested on a daily basis, or supervised feeding of a lower amount, as deemed necessary for full evaluation

The PI/Investigator and family will determine whether to continue daily ingestion, reduce the daily amount, or follow off intervention, and/or refer for additional medical evaluation (i.e., endoscopy).

2. Concern regarding acute symptoms from home ingestion.

Participants will be instructed to contact the PI/Investigator/study team for acute allergic symptoms (with the exception of oral pruritus, mild transient abdominal discomfort, or perioral redness/hives). The investigator will determine the best course of action, with possible actions being the following:

- 1. Continue with daily home dosing
- 2. Return for an observed ingestion of the same amount
- 3. Return for an observed ingestion of a step lower amount.
- 4. Discontinuation of ingestion

The following process algorithm will be applied regarding symptoms associated with the daily ingestion.

If the subject only experiences oral/pharyngeal pruritus, or perioral redness/hives, or mild transient abdominal discomfort, the daily ingestion may continue. Instructions about eating peanut with meals will be reviewed. If the symptoms are bothersome or persistent, procedures per #1 above (chronic symptoms) will be followed.

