symptoms, the observation period should be at least 4 hours and up to 24 hours based on symptoms and treatment regimen needed to stabilize.

3. Excessive days without ingestion of peanut.

Participants will be instructed to skip days ingesting peanut for illness. However, if more than 5 consecutive days are missed, at the discretion of the PI, a visit for observed feeding may be undertaken versus allowing continuation at home.

4. Early withdrawal.

If the PI/Co-I or participant wishes to discontinue participation in the study, they will be asked to attend an early withdrawal visit for review of their diet, collection of diaries, blood, stool and saliva for mechanistic studies and completion of a QOL survey and diet questionnaire.

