### **11.3** Participant Replacement

Participants who withdraw or are withdrawn will not be replaced and will be part of the ITT analysis.

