# **13.7** Sample Size Considerations

The primary objective of this study is to compare the proportion of children who at the desensitization DBPCFC tolerate an amount at least 2 steps higher than the baseline amount or who tolerate the full dose (9043 mg) of peanut protein between the active and the control arm in the HT group. Secondary clinical outcomes of this study include sustained unresponsiveness, skin prick test mean wheal diameters, quality of life, and adverse events. For sample size calculations, we assume a conservative estimate for the proportion of spontaneous tolerance in the control group of 10%. We believe that an additional absolute increase of 45 percentage points under the intervention is feasible and clinically meaningful (55% vs. 10%). We also assume a drop-in rate (avoiders to consumers) and drop-out rate (consumers discontinuing study treatment) of 5% and 20%, respectively. This results in an attenuated effect size of 33.75% percentage points (46% vs. 12.25%). A total of 72 children randomized with equal probability to the active or control arm (36per group) provides approximately 85% power to detect a difference of 33.75% (46% versus 12.25%) in the proportion of children who tolerate at least 2 steps higher amount from baseline or the full amount of peanut protein by the desensitization DBPCFC, based on a 0.05 level continuity corrected chi-squared test. We believe the dropin rate will be kept at a minimum since parents and children will likely not attempt dose escalation on their own. The drop-out rate is conservative, based on our prior experience, which reported a drop-out rate of 15%.

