6.3 Crossover

Crossovers are subjects who after randomization switch from the allocated treatment to the non-allocated treatment. Subjects randomized to peanut ingestion who never consume peanut after the baseline DBPCFC or who permanently discontinue peanut consumption will be considered crossovers. In addition, subjects randomized to avoidance who start ingesting peanut and continue consumption through the desensitization DBPCFC visit (or study discontinuation, whichever comes first) will be considered to have crossed over. Should crossover occur, crossovers will be analyzed as belonging to the group to which they were randomized according to the ITT principle in all efficacy analyses. Safety analyses will be conducted according to the definition of the Safety population described in section 4.

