6.5.1.2 Analysis of Primary Clinical Endpoint

The primary clinical endpoint of this study is the ability to tolerate a dose at least 2 steps higher than the one tolerated at baseline or 9043 mg of peanut protein by the desensitization DBPCFC. The null hypothesis is that there is no difference in the probability of participants who can consume higher amounts of peanut between subjects randomized to ingestion compared to subjects randomized to avoidance. The proportion of subjects in the intervention and the control group meeting the primary outcome will be compared using a continuity corrected chi-squared test at the 0.05 significance level.

As the intent-to-treat principle includes all randomized subjects in the primary analysis, patients who are missing the trial's primary endpoint will have their outcome imputed using multiple imputation assuming that the data are missing at random (MAR). The imputation model will be stratified by randomization assignment and include age, sex, baseline reactive dose strata, clinical severity during baseline DBPCFC as well as peanut-specific IgE levels (log transformed) at baseline and week 16. Since the model includes a mixture of variables types (i.e. continuous and discrete), a fully conditional specification method will be used.²¹ The imputation process will be repeated 30 times to achieve maximal stability of

the procedure. A separate analysis will be conducted for each completed-andimputed dataset. Rubin's rule²² will be used to combine the 30 analyses and test the difference in success rates between the intervention and control groups.

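### The primary imputation model leaves out whether an intervention child permanently stopped peanut, which can modestly overstate the intervention success rate

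*SAP*

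**What the plan says.** **Imputation.** The SAP's primary analysis imputes missing outcomes 30 times under MAR. Section 6.5.1.2 states: "The imputation model will be stratified by randomization assignment and include age, sex, baseline reactive dose strata, clinical severity during baseline DBPCFC". Log peanut-specific IgE at baseline and week 16 completes the list. Protocol 13.4.2 has the same variables, with treatment assignment as a covariate. Neither list has stopping, dose reached or time on peanut.

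**Stoppers who stay in follow-up.** Protocol 8.4 says of children who cannot take 1/16 teaspoon that "they will be considered a treatment failure and will stop any daily ingestion, but will undergo the endpoint DBPCFCs at 72 weeks". Protocol 6.5 keeps other stoppers on study procedures, Protocol 3.1.2 and 8.3 set week 72 as the default challenge time, and Protocol 8.5 gives a window of up to 6 months.

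**Stoppers who leave.** Among the reasons for termination, the synopsis lists the investigator's judgement of the child's best interest and adds "This includes subjects who refuse to come for the Desensitization DBPCFC visit". At early withdrawal, Protocol 8.4 says "they will be asked to attend an early withdrawal visit for review of their diet, collection of diaries, blood, stool and saliva"; no challenge is listed. Protocol 11.3 adds: "Participants who withdraw or are withdrawn will not be replaced and will be part of the ITT analysis".

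**Planning rates.** Protocol 13.7 assumes drop-in and "drop-out rate (consumers discontinuing study treatment) of 5% and 20%, respectively", and calls the 20% conservative, "based on our prior experience, which reported a drop-out rate of 15"%.

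**Status.** SAP 6.3 covers children who never start peanut, and those "who permanently discontinue peanut consumption will be considered crossovers", but uses the definition only to confirm that they are analysed as randomized.

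**The concern.** MAR is conditional on what the model contains. Stopping peanut plausibly predicts both a missing challenge and a poor result. The only post-randomization variable in the model is week-16 IgE, which cannot reflect stopping after week 16. A stopper with no endpoint is therefore treated as exchangeable with same-arm children of similar baseline features and week-16 IgE, most of whom are still eating peanut.

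The sample size calculation takes a different view: it gives stoppers the control success rate. Only the intervention arm has assigned peanut to stop, so if stoppers do worse the error runs one way, towards a larger effect estimate.

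The sensitivity analyses in SAP 6.5.1.3 do not isolate this. Set (b) assigns outcomes by baseline dose in both arms. Item (c) is conditional and names no pattern variable. Item (d) targets the effect of treatment received. Item (e) adjusts for timing and the COVID pause. None imputes by peanut status.

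**Working it through.** **1. The plan's own figures.** From Protocol 13.7 and SAP 6.5.1.1:
- Intervention: 0.80 × 55% + 0.20 × 10% = 46%. Stoppers enter at 10%.
- Control: 0.95 × 10% + 0.05 × 55% = 12.25%. Difference: 33.75 points.
- Power with 36 per arm and the continuity-corrected test: 85.9% by exact enumeration, 84.2% by normal approximation. The stated 85% reproduces.
- SE of the difference: √(0.46 × 0.54/36 + 0.1225 × 0.8775/36) = 9.9 points.

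**2. Bias formula.** Let s be the share of the arm that stops, m the share of stoppers with no endpoint, and p the stoppers' success rate. Continuers succeed at 55%. Suppose only stoppers are missing and the covariates do not separate them from continuers. The imputed rate for a missing stopper is then

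r = [(1−s) × 0.55 + s(1−m) × p] / [(1−s) + s(1−m)],

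and the bias in the arm's rate is s × m × (r − p). Here s is 15% (prior experience) to 20% (plan). The documents do not give m, so it is shown over a range.

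Example with s = 0.20, m = 0.50, p = 0.10: r = (0.44 + 0.01)/0.90 = 50%, and bias = 0.10 × (0.50 − 0.10) = +4.0 points.

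**3. Results (points).**

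| Share of stoppers missing | s = 15%, p = 10% | s = 20%, p = 10% | s = 15%, p = 30% | s = 20%, p = 30% |
|---|---|---|---|---|
| 10% | +0.58 | +0.73 | +0.32 | +0.41 |
| 25% | +1.49 | +1.89 | +0.83 | +1.05 |
| 50% | +3.10 | +4.00 | +1.72 | +2.22 |

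At s = 20%, continuers are 82% (0.80/0.98, m = 10%) to 89% (0.80/0.90, m = 50%) of the observed arm. A missing stopper is filled in at 47 to 50%, against the planned 10%. The number of children affected is 36 × s × m, from 0.5 (15%, 10%) to 3.6 (20%, 50%).

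**4. Simulation check.** With 36 per arm, 30 imputations, the SAP covariate list (drawn unrelated to outcome) and Rubin's rules, the bias was +0.58, +1.51 and +3.07 at s = 15%, and +0.75, +1.95 and +3.99 at s = 20%. When week-16 IgE differed by 1 SD between stoppers and continuers, the bias at s = 20% was still +1.6 (m = 25%) and +3.5 (m = 50%).

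**5. Type I error.** With 12.25% success in both arms, s = 20%, m = 25 to 50%, and stoppers succeeding at 12.25, 5 or 0%, the current model rejected in 1.5 to 2.1% of trials.

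**6. Sensitivity analysis b(i), all missing are failures.** If only stoppers are missing and p = 10%, its error is −s × m × 0.10, from −0.15 to −1.0 points. If 5% of continuers and controls are missing too, the error on the difference is −(s × m × 0.10) − 0.05 × (1−s) × 0.55 + 0.05 × 0.1225, from about −1.8 to −2.6.

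**The case against.** The case for leaving the primary model alone is substantial.

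- **Few children are affected.** The protocol tries to challenge stoppers, and the scenarios above involve 0.5 to 3.6 children. This stands and limits the importance of the point. A reader might take the 15 to 20% as the share with missing endpoints, but Protocol 13.7 defines it as discontinuing treatment.
- **The 10% is a planning device.** It attenuates the effect for power; it does not predict how children do after months of up-dosing. This stands. At 30% the bias nearly halves, and if stoppers do as well as continuers there is none.
- **b(i) already bounds the bias.** In the simplest case it does so well, and conservatively. But it also fails missing controls and continuers, and at 30% stopper success it errs by up to −0.20 × 0.50 × 0.30 = −3.0 points. It is a partial bound.
- **The status may be wrong for the children who matter.** A child eating at last contact who later stops would be coded as a continuer. This stands. If half the missing stoppers were miscoded at s = 20% and m = 50%, an ideal indicator would still leave 0.05 × (0.55 − 0.10) = +2.25 of the +4.0 points. That is a reduction, not a cure.
- **The indicator is sparse.** When at least 3 stoppers are observed, all of them fail in 51 to 66% of trials under the scenarios above. This argues for an augmented fit. It also argues against any rule that switches the primary analysis to control-arm imputation on a data-dependent count.

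**Conclusion.** The point holds as a modest improvement to consider. Both documents omit stopping status from the imputation model, and if stoppers do worse than continuers the intervention success rate is overstated. The size is about +0.3 to +2 points with 10 to 25% of stoppers missing, and up to about +4 with half missing, against an SE of about 10. This rests on 15 to 20% stopping, stopper success of 10 to 30%, continuer success of 55%, and an assumed missing share.

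Two stronger readings are tempting, and the documents support neither.

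- A reader might infer a bias of 0.15 × 0.45 = 6.75 or 0.20 × 0.45 = 9.0 points. That needs every stopper to miss the challenge, whereas Protocol 6.5 and 8.4 keep stoppers in follow-up and Protocol 8.4 expressly schedules a challenge for treatment failures.
- A reader might infer that a positive trial could be spurious. Simulated type I error stays well below 5%; the harm is to the estimate.

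**What to change.** 1. **SAP 6.5.1.2.** Add one indicator to the intervention-arm imputation model: never started or permanently stopped peanut before the endpoint challenge, using the SAP 6.3 status coded at last contact. Fit it with a data-augmented logistic step (weighted pseudo-observations), so that it runs when all observed stoppers fail. Do not add a data-dependent switch to control-arm imputation.
2. **SAP 6.5.1.3.** Add one pre-specified sensitivity analysis that imputes missing outcomes of known stoppers from the control-arm model and leaves all other missing outcomes under MAR.

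Optionally, name the week-72 desensitization challenge among the examples in Protocol 6.5. This is clarification only: that list is illustrative, and other sections already schedule the challenge.

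**Cost.** No new data are needed, but the last-contact coding rule must be written because SAP 6.3 has none. The indicator is sparse in a 36-child arm, and some bias remains. A simulated version that also fell back on control-arm imputation when fewer than 3 stoppers were observed left +0.2, +0.6 and +1.4 points at 20% stopping (10, 25 and 50% missing). Without that fallback, expect somewhat more, and more again where stopping after last contact goes unrecorded.

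The estimate becomes slightly less favourable. At 20% stopping with half of stoppers missing, simulated power is 91.2% under the current model, an inflated figure, and 85.7% with complete data. Two different models using stopping status gave 87.4% (the version with the fallback) and 84%.

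The sensitivity analysis is deliberately pessimistic. In that same setting, if stoppers in fact do as well as continuers, it understates the arm by 0.10 × (0.55 − 0.1225) = 4.3 points, so it belongs beside the primary analysis, not inside it.

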### Escalation Visits (3-8 visits depending upon starting point and progress)

Visits 2 (week 8), 3 (week 16), 4 (week 24), 5 (week 32), 6 (week 40), 7(week 48), 8 (week 56), 9 (week 64) for increasing amounts of peanut (visit length 2-3 hours). These visits stop at week 64 or when 1 Tablespoon (equivalent) is reached.

Attempt to increase daily ingestion by open oral food challenge to next amount higher. Maximum amount is 3 teaspoons/equivalent.

- Physical exam, vital signs, medical history
- Blood samples, Visit 3, week 16 (before feeding challenge commences; not to exceed 5cc/kg on a single day or 9.5ml/kg over any eight-week period per NIH guidelines)
- Spirometry or peak flow (optional under age 7)
- Open oral food challenge to amount determined by DBPCFC (Section 3.1.3) unless at top amount
- Training/review on measuring amounts for home use
- Collection/Provision of diaries and contact instructions
- Saliva and stool collection (visit 3)
- Quality of life survey, diet questionnaire (visit 3)

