### 13.4.2 Primary Analysis of Primary Endpoint(s)/Outcome(s)

The primary endpoint of this study is the ability to tolerate a dose at least 2 steps higher than the one tolerated at baseline or 9043 mg of peanut protein by the desensitization DBPCFC. The proportion of subjects in the intervention and the control group meeting the primary outcome will be compared using a continuity corrected chi-squared test at the 0.05 significance level. As the intent-to-treat principle includes all randomized subjects in the primary analysis, patients who are missing the trial's primary endpoint will have their outcome imputed using multiple imputation techniques. Missing data in the primary endpoint will be assumed to depend only on the observed values, i.e., data are missing at random (MAR). Data imputation under this assumption will be performed using the proposed multiple imputation method by Rubin. Covariates in the imputation model will include treatment assignment, gender, age and baseline reactive dose strata, clinical severity during DBPCFC as well as peanut-specific IgE levels at baseline and week 16.

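### The primary endpoint's imputation model leaves out ladder progress and treatment-stop status, so a missed challenge in the intervention arm is imputed without the child's recorded feeding history

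*SAP*

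**What the plan says.** SAP 6.5.1.2 handles a missing primary endpoint by multiple imputation under missing at random. The model is fitted separately in each randomized arm and contains age, sex, "baseline reactive dose strata, clinical severity during baseline DBPCFC as well as peanut-specific IgE levels (log transformed) at baseline and week 16". Protocol 13.4.2 gives a matching list: "Covariates in the imputation model will include treatment assignment, gender, age and baseline reactive dose strata, clinical severity during DBPCFC", plus the same two IgE measurements. Week-16 IgE is the only predictor measured after randomization.

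The intervention arm produces much more post-baseline information than this. At each escalation visit (Protocol 8.3, every 8 weeks from week 8 to week 64) the task is: "Attempt to increase daily ingestion by open oral food challenge to next amount higher". Protocol 8.4 also defines an outcome for children who cannot take even 1/16 teaspoon: "they will be considered a treatment failure and will stop any daily ingestion". The same sentence goes on to say that they will still have the endpoint challenge at week 72, and Protocol 6.5 keeps children who discontinue peanut in other study procedures.

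The endpoint can nevertheless be missing. Protocol 11.2 foresees children who refuse the desensitization visit, and the early-withdrawal visit in Protocol 8.4 lists no challenge.

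**The concern.** Within the intervention arm, two children who match on the listed predictors receive the same imputed chance of success, even if one stopped at 1/16 teaspoon and the other reached a tablespoon. Week-16 IgE may separate them somewhat, but it is taken before the visits at weeks 24 to 64 and cannot register later stalling or stopping. The documents do not show how well it predicts ladder progress.

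Missing at random is only as credible as the variables it conditions on. If feeding history is related both to missing the challenge and to failing it, leaving it out biases the intervention success rate and hence the primary difference. Controls have no ladder, so the variable exists for one arm only.

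**Working it through.** **1. The plan's own figures.** SAP 6.5.1.1 assumes success of 55% and 10%, 20% of consumers stopping, 5% of avoiders starting, and 36 children per arm.

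- Intervention: 0.80 × 0.55 + 0.20 × 0.10 = 0.46.
- Control: 0.95 × 0.10 + 0.05 × 0.55 = 0.1225. The difference is 33.75 points.
- Power of the continuity-corrected test, two-sided 0.05: 84.2% (Fleiss approximation) or 85.9% (exact enumeration), against about 85% stated.

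The planning figures reproduce.

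**2. What ladder position says about the endpoint.** The cumulative challenge doses in the range that matters are 143, 443, 1043, 2043, 5043 and 9043 mg. Protocol 3.1.3 equates 1 teaspoon of peanut butter with about 1140 mg, so 1/16 teaspoon is about 71 mg and the top of the ladder (3 teaspoons) about 3420 mg.

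| Reacted at (mg) | Tolerated at entry (mg) | Two-step target (mg) | Ladder against target |
|---|---|---|---|
| 443 | 143 | 1043 | passed at 1 tsp (1140) |
| 1043 | 443 | 2043 | passed at 2 tsp (2280) |
| 2043 | 1043 | 5043 | top of ladder below target |
| 5043 | 2043 | 9043 | top of ladder below target |

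Ladder position comes close to settling the endpoint in the first two strata. In the other two it is informative but not decisive. The comparison is approximate, because an open feeding of peanut butter is set against a cumulative blinded dose.

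**3. Bias in closed form.** Let f be the share of stoppers whose endpoint is missing. Assume that all continuing children are observed and that the listed predictors carry no information on stopping. The imputed intervention rate is then the observed-case rate:

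(0.80 × 0.55 + 0.20 × (1 − f) × 0.10) / (0.80 + 0.20 × (1 − f))

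| f (assumed) | Arm missing | Calculation | Imputed rate | Excess over 46% (points) |
|---|---|---|---|---|
| 0 | 0% | 0.460/1.00 | 46.0% | 0 |
| 25% | 5% | 0.455/0.95 | 47.9% | 1.9 |
| 50% | 10% | 0.450/0.90 | 50.0% | 4.0 |
| 75% | 15% | 0.445/0.85 | 52.4% | 6.4 |
| 100% | 20% | 0.440/0.80 | 55.0% | 9.0 |

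At f = 50% the difference from control is 50.0 − 12.25 = 37.75 points instead of 33.75.

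**4. Week-16 IgE and direction.** A simulation of 36 intervention children (1,500 replicates, lightly penalised logistic model) assumed success of 10% in stoppers, 25% in children continuing below a tablespoon and 85% at a tablespoon. Except in the last row, 10% of tablespoon children were missing.

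| Stoppers missing | Assumed IgE link to progress | True | SAP predictors | Ladder added |
|---|---|---|---|---|
| 25% | none | 46.0% | 46.3% | 46.1% |
| 50% | none | 46.3% | 48.7% | 47.6% |
| 75% | none | 45.9% | 50.6% | 49.0% |
| 50% | strong | 46.0% | 47.4% | 47.2% |
| 75% | strong | 45.9% | 49.1% | 48.7% |
| 10%, with 40% of tablespoon children missing | moderate | 45.7% | 40.0% | 42.4% |

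In the runs with 25% to 75% of stoppers missing, the mean imputed chance for a missing stopper and a missing tablespoon child was:

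- SAP predictors, no IgE link: 47–51% for both.
- SAP predictors, moderate link: 44–47% against 49–53%.
- SAP predictors, strong link: 34–38% against 55–57%.
- Ladder added: 26–35% against 66–68%.

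**5. What the sensitivity analyses cover.** Strategy b(i) in SAP 6.5.1.3 counts every missing child as a failure. In the setting of step 3 it gives 45.5%, 45.0% and 44.5% for f = 25%, 50% and 75%, all below 46%.

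**The case against.** The plan intends to observe the children who do badly: Protocol 8.4 schedules treatment failures for the week-72 challenge, and Protocol 8.5 widens the visit window to six months. The 20% in the sample-size section is discontinuation of treatment, not missing endpoints, and no missingness rate is given. All of this stands, and it limits the point to children who do not attend.

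A reader might infer that the planned analysis will overstate the effect. The documents do not support that. The reason for non-return they discuss most is COVID-19, which has no stated link to stalling, and the last row of step 4 shows the bias turning downward when mainly successful children are missing. A reader might also infer that a treatment failure and a tablespoon child will get much the same imputed chance. That holds only if week-16 IgE says little about progress, which the documents leave open.

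SAP 6.5.1.3 gives partial cover. Strategy b(i) guards against upward bias in the intervention arm. The other ad-hoc strategies depend on baseline dose or count every missing child as a success, and methods for data missing not at random are only to be considered, with no trigger. No listed analysis uses the ladder.

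Finally, with about 36 children the model is already full. Stoppers would number about 0.20 × 36 = 7, so few may be observed, and step 4 shows that adding the ladder removes only part of the bias.

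**Conclusion.** The omission is plain in both documents and worth correcting, because the missing variable is already collected and strongly prognostic. Its effect is conditional. If children who stop are more likely to miss the challenge, the intervention rate is overstated by 1.9, 4.0 or 6.4 points for 25%, 50% or 75% of stoppers missing. This rests on the plan's 20%, 55% and 10%, on assumed missingness, and on predictors that say nothing about stopping; an informative week-16 IgE reduces it. If mainly children doing well are missing, the error is downward. If few endpoints are missing, it is negligible. Ladder position should inform the imputation, not replace the endpoint, since it cannot reach the target in the 2043 and 5043 mg strata.

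**What to change.** Before data lock, which is when the SAP allows revision, add to the intervention-arm imputation model in SAP 6.5.1.2 one ordinal term that combines whether the child was still eating peanut with ladder progress at the last attended supervised feeding. For example: stopped or treatment failure; continuing below 1 tablespoon; reached 1 tablespoon. Keep baseline dose stratum in the model, because the same ladder position means different things across strata. Name a penalised or augmented logistic step to avoid separation. The model is already fitted by arm, so a term that exists in one arm only is feasible, and the primary test does not change.

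A ratio of amount tolerated to the child's own target would be a poor choice. The top of the ladder scores 3420/9043 = 0.38 in the 5043 mg stratum, below the 430/1043 = 0.41 of a child in the 443 mg stratum at 3/8 teaspoon.

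The cost is slightly more modelling work and one more parameter in a small arm. The middle category will mix children who stalled with children who left early while progressing. If no stopper is observed, the data cannot inform that category, and strategy b(i) remains the main check.
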